11 ADVERSE EXPERIENCE REPORTING AND DOCUMENTATION

11.1 Adverse Events

An adverse event (AE) is any untoward medical occurrence in a clinical investigation of a patient administered a pharmaceutical product and that does not necessarily have a causal relationship with the treatment. An AE is therefore any unfavorable and unintended sign (including an abnormal laboratory finding), symptom or disease temporally associated with the administration of an investigational product, whether or not related to that investigational product. An unexpected AE is one of a type not identified in nature,

severity, or frequency in the current Investigator’s Brochure or of greater severity or frequency than expected based on the information in the Investigator’s Brochure.

The Investigator will probe, via discussion with the subject, for the occurrence of AEs during each subject visit and record the information in the site’s source documents. Adverse events will be recorded in the patient CRF. Adverse events will be described by duration (start and stop dates and times), severity, outcome, treatment and relation to study drug, or if unrelated, the cause.

AE Severity

The National Cancer Institute’s Common Terminology Criteria for Adverse Events (CTCAE) Version 3.0 should be used to assess and grade AE severity, including laboratory abnormalities judged to be clinically significant. The modified criteria can be found in the study manual. If the experience is not covered in the modified criteria, the guidelines shown in Table 3 below should be used to grade severity. It should be pointed out that the term “severe” is a measure of intensity and that a severe AE is not necessarily serious.

Table 3. AE Severity Grading

| Severity (Toxicity Grade) | Description |
|----------------------------------|---|
| Mild (1) | Transient or mild discomfort; no limitation in activity; no medical intervention or therapy required. The subject may be aware of the sign or symptom but tolerates it reasonably well. |
| Moderate (2) | Mild to moderate limitation in activity, no or minimal medical intervention/therapy required. |
| Severe (3) | Marked limitation in activity, medical intervention/therapy required, hospitalizations possible. |
| Life-threatening (4) | The subject is at risk of death due to the adverse experience as it occurred. This does not refer to an experience that hypothetically might have caused death if it were more severe. |

AE Relationship to Study Drug

The relationship of an AE to the study drug should be assessed using the following the guidelines in Table 4.

Table 4. AE Relationship to Study Drug

| Relationship to Drug | Comment |
|-----------------------------|---|
| Definitely | Previously known toxicity of agent; or an event that follows a reasonable temporal sequence from administration of the drug; that follows a known or expected response pattern to the suspected drug; that is confirmed by stopping or reducing the dosage of the drug; and that is not explained by any other reasonable hypothesis. |
| Probably | An event that follows a reasonable temporal sequence from administration of the drug; that follows a known or expected response pattern to the suspected drug; that is confirmed by stopping or reducing the dosage of the drug; and that is unlikely to be explained by the known characteristics of the subject’s clinical state or by other interventions. |

| | |
|-----------|---|
| Possibly | An event that follows a reasonable temporal sequence from administration of the drug; that follows a known or expected response pattern to that suspected drug; but that could readily have been produced by a number of other factors. |
| Unrelated | An event that can be determined with certainty to have no relationship to the study drug. |

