2.1 Risk / Benefit Assessment

Risk: Inhaled n-acetylcysteine (NAC) is approved for the treatment of mucus associated airway disease, including asthma. The main side effect from inhaled n-acetylcysteine (NAC) is bronchospasm. We find that co-administering NAC and albuterol effectively prevents excessive bronchoconstriction in asthmatic patients. Specifically, in ten asthmatics that were given doses of 20% NAC as high as 3 mL together with 3 mL of albuterol, the largest FEV1 decline was 6%.

Benefit: Mucus plugs cause airway obstruction and symptoms of dyspnea. The role of mucolytics in decreasing plugs and increasing FEV1 has not been well studied. Our preliminary data, utilizing CT imaging and a novel scoring system, can identify and target a subgroup of patients who may benefit from inhaled mucolytic treatment more so than the asthmatic population as a whole.

To minimize risk, study participants will be admitted to a medical-surgical ward in the hospital and given all treatments under the supervision of a registered nurse and the covering medical team. Our study team of experienced clinicians will be available as needed.

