14 DATA SAFETY MONITORING

Adverse events will be monitored by the Clinical PIs (Drs. [name], [name] and [name]) in real-time. Safety and tolerability data will be summarized quarterly. Adverse event rates will be coded by body system and MedDra classification term. Adverse events will be tabulated and will include the number of patients for whom the event occurred, the rate of occurrence, and the severity and relationship to study drug. All AEs will be reviewed quarterly in the regularly scheduled quality assurance meetings of UCSF Airway Clinical Research Center, which is attended by Drs. [name], [name], [name] and [name].

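### Table 4 lets a known toxicity be coded Definitely related with no condition on timing or other cause, and leaves some events with no row; the effect is confined to the relationship column of the AE tables

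*Protocol*

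**What the plan says.** Protocol section 11.1 introduces the causality scale with "The relationship of an AE to the study drug should be assessed using the following the guidelines in Table 4". The table has four levels.

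- *Definitely* begins "Previously known toxicity of agent; or an event that follows a reasonable temporal sequence from administration of the drug". After a condition on familiar response pattern, it ends "that is confirmed by stopping or reducing the dosage of the drug; and that is not explained by any other reasonable hypothesis".
- *Probably* requires timing, a familiar pattern and confirmation by stopping or reducing the drug, and an event "that is unlikely to be explained by the known characteristics of the subject’s clinical state or by other interventions".
- *Possibly* requires timing and a familiar pattern, "but that could readily have been produced by a number of other factors".
- *Unrelated* is "An event that can be determined with certainty to have no relationship to the study drug".

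There is no level between *Possibly* and *Unrelated*, and none for events that cannot be assessed.

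Section 2.1 states: "The main side effect from inhaled n-acetylcysteine (NAC) is bronchospasm". Section 5.3 makes NAC-induced bronchoconstriction the foremost safety concern and monitors it by peak flow around each treatment. AEs are captured throughout the study (9.1.17) and SAEs from consent to the final visit (11.2.1). Section 14 says the AE tables will include "the rate of occurrence, and the severity and relationship to study drug". The SAP has no rules for AEs.

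**The concern.** In the *Definitely* row, every qualifying condition describes the event named after the *or*. A known toxicity stands before the *or* and carries no condition. In this population the best-known toxicity of the drug is also a manifestation of the disease, and several study procedures can provoke it. A literal rater could therefore book disease-related or procedure-related bronchospasm as definitely drug-related.

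At the other end, both *Probably* and *Possibly* demand a familiar pattern and *Unrelated* demands certainty. An unexpected drug effect with plausible timing cannot be entered even as possibly related. An event that is unlikely, but not certainly, due to the drug has no entry either.

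The trial has one arm, so no comparator in the AE tables separates drug effect from background asthma. The relationship column is the only part of those tables that attempts the separation.

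**Working it through.** No figure in the plan is at issue. The check is on the logic of Table 4 and on whether the study schedule produces the problem cases.

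**Step 1: write the table as rules.** Let K = known toxicity, T = reasonable timing, P = familiar pattern, D = confirmed by stopping or reducing, and A = other explanation (none, unlikely, readily available). K is taken to imply P.

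| Level | Rule |
|---|---|
| *Definitely*, reading (a), plain | K, or (T and P and D and A = none) |
| *Definitely*, reading (b), softer: K replaces only timing | (K or T) and P and D and A = none |
| *Probably* | T and P and D and A = none or unlikely |
| *Possibly* | T and P and A = readily available |
| *Unrelated* | certainly no relationship |

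Leaving aside events that are certainly unrelated, there are 2 × 2 × 2 × 3 = 24 profiles without K (T, P, D, A) and 2 × 2 × 3 = 12 with K (T, D, A), 36 in all. These are logical combinations, not event frequencies.

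**Step 2: known toxicities such as bronchospasm (12 profiles).**

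- Reading (a): all 12 are *Definitely*, including all 6 without reasonable timing. Two of the 12 (timing fits, another cause readily available) also meet *Possibly*, so the levels overlap.
- Reading (b): of the 6 without timing, 1 is *Definitely* and 5 have no row. Of the 6 with timing, 2 have no row (no confirmation by stopping, no readily available other cause). That is 7 of 12 without a row.

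Neither reading handles these events well: (a) over-attributes, (b) leaves gaps.

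**Step 3: all other events (24 profiles).** Only 4 have a row: T, P and D with A = none or unlikely (2 profiles), and T and P with A = readily available, with or without D (2 profiles). So 24 − 4 = 20 have none. Among the 12 with reasonable timing, 12 − 4 = 8 have none: 6 with an unfamiliar pattern, and 2 with a familiar pattern, no confirmation by stopping and no readily available other cause. This result is the same under both readings.

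**Step 4: does the schedule produce such events?**

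- Before the first dose: methacholine challenge at optional Visit 2b (Day −7), where section 9.1.11 lists severe bronchoconstriction as a rare risk. Sputum induction also takes place at Visit 3 (Day −5).
- After the last dose: sputum induction at Visit 11 (Day 48), where section 9.1.12 lists a severe asthma attack as a rare risk. Dosing ends on Day 5, so this is 48 − 5 = 43 days later.
- Off-drug time from Day 1 to Day 91: (91 − 5)/91 = 94.5% of days. Appendix 1 schedules peak-flow monitoring on Days 1-5 only.

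A pre-dose reaction in someone who is later dosed literally meets *Definitely*. It also meets *Unrelated*, since no drug had been given, and the table does not say which row prevails.

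**The case against.** The strongest reply is that the main safety question does not depend on Table 4. Section 5.3 answers it with peak flow before and after each treatment, and the visit lists schedule this on every dosing day. The synopsis's safety evaluation is AE incidence, which needs no rating. Section 17.2 has SAEs go to the IRB regardless of causality, and section 12.1 rests discontinuation on judgement. All of this stands. A reader might infer from the wording that bronchospasm attribution will be wrong and the main safety question lost; the documents do not support that.

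Table 4 is also presented as guidance, applied by clinicians who review AEs in real time. Section 11.1 defines an AE by its temporal association with the product and asks for the cause of unrelated events. A sensible rater may well code a Day 60 asthma attack as unrelated. This makes miscoding less likely, but the row still permits it, and AEs are collected well outside the dosing days.

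Three further inferences fail.

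- The 94.5% is a share of days, not of events or of miscoded events.
- Events on Days 4-5 cannot be said to lack confirmation by stopping: dosing ends for everyone after Day 5, with assessments on Days 6 and 13.
- Under the plain reading the missing rows do not touch bronchospasm, which always has one. They affect it only under the softer reading.

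**Conclusion.** The point holds as a drafting defect with limited reach. Read plainly, *Definitely* is met by any known toxicity without regard to timing or other cause, so bronchospasm before the first dose or weeks after the last can be coded definitely related. Independently of that reading, 20 of 24 profiles that are neither a known toxicity nor certainly unrelated have no row, and 8 of 12 have none even when timing is reasonable.

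The exposure is the relationship column described in section 14. Peak-flow monitoring, AE incidence, SAE reporting to the IRB and the efficacy analyses are untouched. The documents give no event rates, so the share of events affected cannot be stated.

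The conclusion assumes that raters follow the row as written; the profile counts assume that a known toxicity has a familiar pattern. The correction is worth making because it is cheap and because a single-arm trial has no control group to put the ratings in context.

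**What to change.** 1. In the *Definitely* row, delete the opening clause on known toxicity up to and including the first *or*, so that the timing and alternative-cause conditions apply to known toxicities too.
2. Define *Possibly* as reasonable timing where a drug cause cannot be excluded, with no requirement for a familiar pattern or a ready alternative. Dropping only the pattern requirement is not enough: a novel, well-timed event with no other ready cause would still have no row.
3. Add *Unlikely*, defined for example as timing that does not fit, but without certainty that the drug played no part. State that the highest row met applies. All 36 profiles then have one row: the 18 with reasonable timing fall in *Possibly* or above, and the 18 without it in *Unlikely*.
4. Tabulate bronchospasm by period (before first dose, Days 1-6, after Day 6) whatever its rating.

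The cost is a wording amendment to one table and the AE form, with IRB approval under section 17.1; events already rated would need re-rating. Item 4 needs no new data and can be done even if the table stays as it is: section 9.1.17 records event start and stop dates and times, and section 8.6 records dosing dates and times.

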11.2 Serious Adverse Experiences (SAE)

An SAE is defined as any AE occurring at any dose that results in any of the following outcomes:

- death
- a life-threatening adverse experience
- inpatient hospitalization or prolongation of existing hospitalization
- a persistent or significant disability/incapacity
- a congenital anomaly/birth defect

Other important medical events may also be considered an SAE when, based on appropriate medical judgment, they jeopardize the subject or require intervention to prevent one of the outcomes listed.

11.2.1 Serious Adverse Experience Reporting

Study sites will document all SAEs that occur (whether or not related to study drug) per [UCSF CHR Guidelines](#). The collection period for all SAEs will begin after informed consent is obtained and end after procedures for the final study visit have been completed.

In accordance with the standard operating procedures and policies of the local Institutional Review Board (IRB)/Independent Ethics Committee (IEC), the site investigator will report SAEs to the IRB/IEC.

12 DISCONTINUATION AND REPLACEMENT OF SUBJECTS

12.1 Early Discontinuation of Study Drug

A subject may be discontinued from study treatment at any time if the subject, the investigator, or the Sponsor feels that it is not in the subject's best interest to continue. The following is a list of possible reasons for study treatment discontinuation:

Subject withdrawal of consent

Subject is not compliant with study procedures

Adverse event that in the opinion of the investigator would be in the best interest of the subject to discontinue study treatment

- Protocol violation requiring discontinuation of study treatment
- Lost to follow-up
- Sponsor request for early termination of study
- Positive pregnancy test (females)

If a subject is withdrawn from treatment due to an adverse event, the subject will be followed and treated by the Investigator until the abnormal parameter or symptom has resolved or stabilized.

All subjects who discontinue study treatment should come in for an early discontinuation visit as soon as possible and then should be encouraged to complete all remaining scheduled visits and procedures.

All subjects are free to withdraw from participation at any time, for any reason, specified or unspecified, and without prejudice.

Reasonable attempts will be made by the investigator to provide a reason for subject withdrawals. The reason for the subject's withdrawal from the study will be specified in the subject's source documents. Refer to Section 10 for early termination procedures.

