6.3 Exclusion Criteria

1. Pregnant, breastfeeding, or unwilling to practice birth control during participation in the study.
2. Presence of a condition or abnormality that in the opinion of the Investigator would compromise the safety of the patient or the quality of the data.
3. Smoking of tobacco or other recreational inhalants in last year and/or >10 pack-year smoking history
4. Current participation in an investigational drug trial
5. Other chronic pulmonary disorders, including (but not limited to) cystic fibrosis, chronic obstructive pulmonary disease, chronic bronchitis, vocal cord dysfunction (that is the sole cause of respiratory symptoms and at the PI's discretion), severe scoliosis or chest wall deformities that affect lung function, or congenital disorders of the lungs or airways
6. Unwillingness to follow study procedures
7. History of allergy or intolerance to study drug
8. Any other criteria that places the subject at unnecessary risk according to the judgment of the Principal Investigator

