9.1.14 CT Imaging of the Thorax

A single inspiratory low dose CT scan of the thorax using a model based iterative reconstruction (MBIR) approach will be taken at the baseline eligibility visit (Visit 2) and following the treatment period over 3 months (Visit 9, 11 and 12).

The risks associated with CT scanning are that of the additional amount of radiation exposure. The additional amount of radiation that each participant will receive as a result of participating in this study will be approximately 5 mSv, which is slightly greater than the yearly natural background of radiation in the US, which is 3 mSv. This amount of radiation may involve a low risk of cancer. A participant should not participate in this study if she is pregnant or breastfeeding.

Additional risks are associated with the uncovering of abnormal findings. There is a risk of possible detection of an abnormality in the lung, which after testing or treatment, is found not to be disease causing. This includes possible misdiagnosis of lung cancer. Such findings may result in unnecessary anxiety for the participant, and increase his or her chance that an outpatient physician may believe that the abnormality is lung cancer and order further testing. This testing could include additional CT scans with additional radiation exposure, other types of scans to determine if the abnormalities are rapidly growing, a needle biopsy (taking a sample of the abnormality with a needle) or a lung biopsy, which requires surgery. Whether these additional studies would be performed would be a decision that the participant would make with his or her regular physician.

In an effort to minimize risk to participants, scans will be read by radiologists that have expertise in interpreting findings of chest CTs. If there are any abnormalities, other than those that are usually found in asthmatic patients, observed by the clinical center radiologists, these would be reported to the principal investigator, who will in turn communicate these findings to the participant. The most likely abnormal result will be the identification of a spot on the lung that might be cancer.

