10.14 Early Withdrawal Visit (Before end of Visit 3)

1. Record any adverse experiences.
2. Record changes to concomitant medications.
3. Perform and record vital signs.
4. Perform and record oximetry.
5. Perform abbreviated physical examination.
6. Perform and record spirometry.

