10.15 Late Withdrawal Visit (After Visit 3 Completion)

1. Record any adverse experiences.
2. Record changes to concomitant medications.
3. Perform and record vital signs.
4. Perform and record oximetry.
5. Perform abbreviated physical examination.
6. Perform and record fractional exhaled nitric oxide (FeNO) measurement.
7. Perform and record spirometry.
8. Perform and record post-bronchodilator reversibility.
9. Collect blood sample for clinical laboratory tests.
10. Obtain a CT scan of the thorax.

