12.2 Withdrawal of Subjects from the Study

A subject may be withdrawn from the study at any time if the subject, the investigator, or the Sponsor feels that it is not in the subject's best interest to continue.

All subjects are free to withdraw from participation at any time, for any reason, specified or unspecified, and without prejudice.

Reasonable attempts will be made by the investigator to provide a reason for subject withdrawals. The reason for the subject's withdrawal from the study will be specified in the subject's source documents. As noted above, subjects who discontinue study treatment early (i.e., they withdraw prior to Visit 8) should have an early discontinuation visit. Refer to Section 10 for early termination procedures. Subjects who withdraw after Visit 8 but prior to Visit 11 should be encouraged to come in for a final visit (and the procedures to be followed would include those for their next scheduled visit).

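### The Late Withdrawal Visit orders a thorax CT with no pregnancy test before it, and section 12.1 makes no exception for a participant who stops drug because she is pregnant

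*Protocol*

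**What the plan says.** Protocol 10.15 has ten items for a participant who leaves after Visit 3. The tenth is "Obtain a CT scan of the thorax", and none of the ten is a pregnancy test. Section 10.14, for those who leave before the end of Visit 3, has neither a CT nor a pregnancy test.

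Section 12.1 includes a positive pregnancy test among the possible reasons for stopping study drug. It asks all who stop to attend an early discontinuation visit, and says they "then should be encouraged to complete all remaining scheduled visits and procedures". It refers to Section 10 for the procedures. Section 12.2 repeats that "subjects who discontinue study treatment early (i.e., they withdraw prior to Visit 8) should have an early discontinuation visit". It adds that a participant who withdraws after Visit 8 and before Visit 11 should have a final visit with the procedures of the next scheduled visit.

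Two places bear on pregnancy and radiation. Exclusion criterion 1 in 6.3 reads "Pregnant, breastfeeding, or unwilling to practice birth control during participation in the study". Section 9.1.14, directly after describing the radiation risk of CT, says "A participant should not participate in this study if she is pregnant or breastfeeding". Section 9.1.13 calls for urine tests before and during participation and leaves the timing to Appendix 1. Appendix 1 marks tests at Visits 1, 2, 3, 9, 10, 11 and 12, and has no column for a withdrawal visit.

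**The concern.** Everywhere else the protocol tests and then scans. At the late withdrawal visit it scans without testing. A participant of childbearing potential who stops during the inpatient days could therefore have a thorax CT on the strength of a test done before her first dose.

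The second strand is the participant who stops because she is known to be pregnant. Section 12.1 treats her like any other discontinuation: a visit whose list, by timing, ends in a CT, and then encouragement to continue with a schedule that contains more CTs. No sentence tells staff to leave the scan out. At stake is avoidable fetal radiation exposure, which 9.1.14 evidently means to prevent.

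**Working it through.** No sample size, power or error rate enters this point, so the check is a comparison of lists and dates.

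**1. Lists with a CT.** The number shown is the item's position in each list.

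| Section 10 list | Urine pregnancy test | CT |
|---|---|---|
| 10.2, Visit 2 | 4 | 7 |
| 10.3, Visit 2b (optional) | 4 | 7 |
| 10.10, Visit 9 | 5 | 10 |
| 10.12, Visit 11 | 3 | 7 |
| 10.13, Visit 12 | 3 | 7 |
| 10.15, Late Withdrawal Visit | none | 10 |

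Five of the six lists have a test, always before the CT. The exception is 10.15. Section 9.1.13 does not fill the gap, because the schedule it relies on covers Visits 1 to 12 only.

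**2. Which list applies after stopping drug.** Section 10 has no visit called an early discontinuation visit. Drug is first given at Visit 4, and 10.14 ends with Visit 3, so by timing only 10.15 fits. This mapping is an inference from the section titles.

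**3. Who is exposed to the gap.**
- Stops after Visit 3 and before Visit 9: the last scheduled test was at Visit 3, and 10.15 applies. Those who leave between Visits 8 and 9 are an exception, since 12.2 gives them the Visit 9 list.
- Withdraws after Visit 8 and before Visit 11: under 12.2 the next visit's list applies. Visits 9 and 11 test before the CT, and Visit 10 has no CT. The gap is closed.
- Withdraws after Visit 11: 12.2 is silent, so 10.15 applies by its title. The last scheduled test was at Visit 11, which is at most 93 − 46 = 47 days before the latest date for Visit 12.

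The first group is the main one.

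**4. Interval between the scheduled tests around dosing.** Visit 3 is Day −5 ± 2, that is Day −7 to Day −3. Visit 9 is Day 6.
- If there is a Day 0: 6 − (−3) = 9 to 6 − (−7) = 13 days.
- If there is no Day 0: one day fewer, 8 to 12 days.

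So the two tests are about 8 to 13 days apart, and none is scheduled between them.

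**5. The instruction after a positive test.** Section 12.1 applies its follow-up sentence to everyone who stops and exempts no one. The CTs that remain on the schedule after dosing starts are at Visits 9, 11 and 12 (9.1.14). Each follows a test, but no section says what to do about the CT if that test is positive. Section 9.1.14 says who should not take part, and gives no instruction for a pregnancy found during the study.

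**The case against.** The protocol is not silent. Section 9.1.14 places its sentence on pregnancy right after the radiation risk, and a sensible investigator would read it as a bar to scanning. The sentence in 12.1 is general retention wording. It covers participants who are lost to follow-up or have withdrawn consent, for whom completing everything is impossible, so it cannot be meant literally for every reason. The language is permissive, and 12.2 lets the investigator withdraw anyone. All of this stands, and it is why the point is minor. It does not supply the missing test in 10.15, and withdrawal after Visit 3 is the very route that leads to 10.15.

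Stronger readings are tempting but not supported:

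- A reader might infer that the protocol requires a pregnant participant to be scanned. It does not. It encourages completion and omits an exception.
- A reader might count up to four CTs after stopping drug: the one in 10.15 plus Visits 9, 11 and 12. That treats one person as both withdrawn and continuing. Section 10.15 is a withdrawal visit, and 12.2 equates early discontinuation with withdrawing. The last three CTs each follow a test in any case.
- A reader might see a defect in having no test at Visits 4 to 8. The protocol ties pregnancy to methacholine (9.1.11) and to CT radiation (9.1.14). Neither is scheduled on those days, and the documents state no fetal risk from NAC. Section 12.1 gives only possible reasons for stopping, so it need not be matched to a scheduled test.
- Appendix 1 marks a test at Visit 10 that 10.11 omits. Visit 10 has no drug and no CT, so this is a clerical mismatch.

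**Conclusion.** The point holds in a narrow form. One of the six lists with a CT, 10.15, lacks the pregnancy test that the other five place before the scan, and 12.1 gives no exception or instruction for a participant who is pregnant. Followed as written, the protocol permits an untested CT, or a CT in a known pregnancy, in tension with 9.1.14.

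The size is small. The gap mainly concerns participants of childbearing potential who stop between Visit 3 and Visit 9. The documents give neither the number of such participants among the 30 nor an expected rate of withdrawal, so no count can be offered. The FEV1 analysis is unaffected. The conclusion assumes that the early discontinuation visit in 12.1 and 12.2 is the Late Withdrawal Visit. If the sponsor meant another set of procedures, the protocol should name it; 10.15 would still need the test.

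**What to change.** 1. In 10.15, add a urine pregnancy test before the CT, for participants of childbearing potential.
2. In 9.1.14 and 12.1, state that every study CT in a participant of childbearing potential, including the one in 10.15, requires a negative test. State also that a participant found to be pregnant receives no further study drug or CT but keeps the safety follow-up that involves no radiation.

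The cost is wording in three sections and one extra point-of-care urine test, only for those who have a late withdrawal visit. Anyone found pregnant will lack a later CT score. If the missing scan is the end-of-treatment one, she has no pair for the SAP's t-test on the CT mucus score. Section 12.3 already provides for replacing participants who withdraw from treatment or from the study.

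A test at Visit 4 before the first dose is optional. The Visit 10 entries in 10.11 and Appendix 1 can be aligned in the same amendment as a clerical correction.
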